
A secondary objective of this study is to evaluate the safety of fremanezumab in adult patients with ECH.
	
The secondary safety endpoints are as follows:
 
 • occurrence of adverse events throughout the study • clinical laboratory (serum chemistry, hematology, coagulation, and urinalysis) test results at each visit • vital signs (systolic and diastolic blood pressure, oral temperature, and pulse rate) measurements at each visit. Note: Oxygen saturation will be measured in cases of suspected anaphylaxis and severe hypersensitivity. Respiratory rate will also be measured in these cases but not as a standard vital sign. • 12-lead electrocardiogram (ECG) findings at screening, baseline, and week 12 • use of concomitant medication during the study • clinically significant changes in physical examinations, including body weight • injection site reaction (ie, erythema, induration, and ecchymosis) and injection site pain assessments • occurrence of hypersensitivity/anaphylaxis reactions • suicidal ideation and behavior as measured by the electronic Columbia Suicide Severity Rating Scale (eC-SSRS)

The immunogenicity objective is to evaluate the immunogenicity of fremanezumab and the impact of antidrug antibodies (ADAs) on clinical outcomes in patients exposed to iv and sc fremanezumab
	
The immunogenicity endpoints are ADA incidence and characteristics (eg, titer, kinetics, and neutralizing activities)

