- ^u Responses at week 1 will be recorded in the electronic diary device at home, and responses at all other time points will be entered into the investigational site tablet.
- ^v Patients will return the wearable sensor if they do not rollover into the long-term safety study (Study TV-48125-CNS-30058) or if they rollover into the long-term safety study but do not wish to continue participating in the wearable sensor substudy.
- ^w The eC-SSRS Baseline/Screening version will be completed at visit 1, and the eC-SSRS Since Last Visit version will be completed at all other visits, including unscheduled visits. Results from both versions will be entered into the investigational site tablet.
- ^x Patients randomized to the 900-mg iv loading dose group will receive 900 mg of fremanezumab administered via an approximately 1-hour iv infusion followed by placebo as 3 sc injections at visit 2 (week 0) and fremanezumab at 225 mg administered as single sc injections (225 mg/1.5 mL) at visits 3 and 4 (weeks 4 and 8, respectively). Patients randomized to the fremanezumab 675-mg sc quarterly group will receive placebo administered via an approximately 1-hour iv infusion followed by fremanezumab at 675 mg administered as 3 sc injections (225 mg/1.5 mL) at visit 2 (week 0) and placebo administered as single sc injections at visits 3 and 4 (weeks 4 and 8, respectively). Patients in the placebo group will receive placebo administered via an approximately 1-hour iv

Clinical Study Protocol with Amendment 02

infusion followed by placebo administered as 3 sc injections at visit 2 (week 0) and placebo administered as single sc injections at visits 3 and 4 (weeks 4 and 8, respectively).

^y Patients will be assessed for hypersensitivity reactions and anaphylaxis during and after administration of the IMP (through 1 hour postdose).

^z Injection site will be assessed for erythema, induration, ecchymosis, and pain immediately (+10 minutes) and 1 hour (± 15 minutes) after IMP administration. If a patient has severe injection site induration, erythema, ecchymosis, or pain at 1 hour after completion of IMP administration, the patient will be reassessed 3 hours (± 15 minutes) after completion of IMP administration and hourly (± 15 minutes) thereafter until the reaction is of moderate or less severity.

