7.11. Injection Site Assessments

Injection site assessments will be performed immediately (+10 minutes) and 1 hour (±15 minutes) after receiving each dose of the IMP. The injection site(s) will be assessed for erythema, induration, and ecchymosis.

Severity will be graded according to the following criteria:

- Injection site erythema, induration, and ecchymosis will be graded according to measurements: absent, 5 to ≤50 mm (mild), >50 to ≤100 mm (moderate), and >100 mm (severe). Induration must be assessed by careful superficial palpation avoiding pressuring or squeezing the injection site.
- For spontaneous report of local pain after the injection, it will be measured as summarized in Table 5.

Table 5: Severity of Pain Scale for Injection Site Assessments

Symptom	Severity grade	Assessment
Pain	0	Absent
	1	Mild
	2	Moderate
	3	Severe

If a patient has severe injection site induration, erythema, ecchymosis, has severe injection site induration, erythema, ecchymosis, or pain at 1 hour after completion of IMP administration, the

patient will be reassessed at 3 hours (± 15 minutes) after completion of IMP administration and hourly (± 15 minutes) thereafter until the reaction is of moderate or less severity.

Appropriate treatment may be provided if necessary, in which case it must be recorded as concomitant medication.

Injection-site reactions (injection site erythema, induration, ecchymosis, and pain) should be recorded as adverse events.

8. ASSESSMENT OF PHARMACOKINETICS/BIOMARKERS/ PHARMACOGENOMICS/IMMUNOGENICITY/ANCILLARY STUDIES

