After completing predose assessments, patients will be treated with IMP. Refer to Section 5.1.1.1 for details regarding IMP administration. A 4-mL blood sample for pharmacokinetics analysis will be collected at the end of the IMP infusion (+10 minutes) from the arm that is not used for the IMP infusion.

The following procedures and assessments will be performed at visit 2 (week 0) after dosing:

- Perform local injection site assessment immediately (+10 minutes) and at 1 hour (± 15 minutes) after completing IMP administration. Additional injection site assessments may be performed based on the severity of any observed injection site reaction. See Section 7.11 for additional details.
- Evaluate for anaphylaxis and hypersensitivity reactions.
- Inquire about postdose adverse events before the patient leaves the study center.

Week 1 (Day 7)

Patients will complete the PGIC scale and the PPSI at 1 week after receiving IMP using the electronic diary device.

Visit 3 (Week 4 [Day 28+3 Days])

The following predose procedures and assessments will be performed at visit 3:

- Review study compliance.
- Review electronic diary data.
- Perform vital signs measurements (includes systolic and diastolic blood pressure, pulse, and body temperature).
- Inquire about adverse events.
- Inquire about concomitant medications.
- Perform clinical laboratory tests (serum chemistry, hematology, coagulation, and urinalysis).
- Perform urine β -HCG pregnancy test (for women of childbearing potential only).
- Obtain a 4-mL blood sample for pharmacokinetics analysis from either arm.
- Obtain a 5-mL blood sample for ADA analysis.
- Administer the HADS, EQ-5D questionnaire, SF-12, and WPAI questionnaire.

- Each patient’s partner/family member completes the Impact on Partner and Family questionnaire. Partners/family members will be asked to attend the study visit with the patient. Partners/family members will be asked to attend the study visit with the patient or to return to the investigational center within ± 3 days of the patient’s visit if unable to appear at the same time.
- Complete the PPSI.
- Complete the PGIC scale.
- Complete the eC-SSRS Since Last Visit version.
- Perform wearable sensor device check and compliance check for patients enrolled in the wearable sensor substudy.

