8.4. Injection Site Assessments

Injection site assessments will be performed immediately (+10 minute) and 1 hour (± 15 minutes) after receiving each dose of the IMP at visits 2, 3 and 4. The injection site(s) will be assessed for erythema, induration, and ecchymosis. More details are in Section 7.11 of the study protocol.

Injection-site reactions should be recorded as adverse events. Injection-site related adverse events will be summary as indicated in Section 8.3.

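### Injection site pain is a named safety endpoint, but the protocol gives two ways of ascertaining it: scheduled in Table 2, on spontaneous report in Section 7.11

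*Protocol*

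**What the plan says.** Among the secondary safety endpoints, protocol Section 2.1 lists "injection site reaction (ie, erythema, induration, and ecchymosis) and injection site pain assessments". SAP Section 1.3 repeats this. Pain is thus named separately from the three visible or palpable signs.

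The schedule in protocol Section 3.5 (Table 2, footnote z) reads: "Injection site will be assessed for erythema, induration, ecchymosis, and pain immediately (+10 minutes) and 1 hour" after administration. Table 2 marks the assessment at visits 2, 3 and 4.

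Section 7.11 sets the same two times but names only erythema, induration and ecchymosis as the things assessed. On pain it says: "For spontaneous report of local pain after the injection, it will be measured as summarized in Table 5". Its rule for further checks then applies to a severe sign "or pain at 1 hour after completion of IMP administration". On recording, it adds: "Injection-site reactions (injection site erythema, induration, ecchymosis, and pain) should be recorded as adverse events".

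SAP Section 8.4 follows Section 7.11: "The injection site(s) will be assessed for erythema, induration, and ecchymosis. More details are in Section 7.11 of the study protocol". Appendix B of the protocol names no signs for the visit procedures and also points back: "Additional injection site assessments may be performed based on the severity of any observed injection site reaction. See Section 7.11 for additional details".

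**The concern.** A site working from the schedule checks every patient for pain twice after each dose. A site working from Section 7.11 checks for three signs and grades pain when a patient raises it. Both texts are current, and both can be followed in good faith.

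Scheduled and unprompted ascertainment give the same incidence only if every patient with pain mentions it unprompted. Otherwise the pooled rate is a mixture whose composition nobody can reconstruct afterwards. Injection site pain is already listed as an identified adverse drug reaction in protocol Section 1.3.1, and about 80 centres are planned (Section 3.2). What is at stake is the meaning of the absolute pain rate and its consistency between sites. No efficacy conclusion is affected.

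**Working it through.** The plan states no pain rate, so there is no figure to reproduce. The check is a comparison of current passages.

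| Place | Scheduled items | Treatment of pain |
|---|---|---|
| Protocol 2.1, SAP 1.3 | not applicable | a named safety endpoint, separate from the other signs |
| Protocol Table 2, footnote z | four, including pain | assessed at both times, visits 2, 3 and 4 |
| Protocol 7.11, list and grading | three, without pain | graded on spontaneous report |
| Protocol 7.11, reassessment rule | not applicable | relies on severe pain at 1 hour |
| Protocol Table 5 | not applicable | grades 0 to 3, with 0 meaning absent |
| Protocol Appendix B | none named | refers to 7.11 |
| SAP 8.4 | three, without pain | not mentioned; refers to 7.11 |

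**Step 1: is there a conflict?** Yes. Footnote z and Section 7.11 share the same times and differ on whether pain is on the list.

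**Step 2: does Section 7.11 settle it?** Not cleanly. Its 1-hour rule and the absent grade in Table 5 both sit more naturally with a scheduled check, because a spontaneous report of pain would not ordinarily yield a grade of absent.

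**Step 3: does the SAP settle it?** No. Its Introduction lets the SAP prevail where it differs from the protocol, but that governs analysis. It does not tell site staff which of two protocol passages to apply.

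**Step 4: how do the data reach the analysis?** Section 7.11 records injection site reactions, including pain, as adverse events, and SAP Section 8.3 summarises injection site events overall and by severity and lists them. SAP 8.4 plans nothing beyond that summary. The scheduled pain grades that footnote z calls for have no stated tabulation.

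**Step 5: direction of the effect, by illustration only.** Let p be the incidence found by scheduled assessment, s the share of those patients whose pain is recorded without a pain-specific check, and f the share of patients at sites following footnote z. Then

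recorded incidence = p × [f + (1 − f) × s].

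The documents give none of p, s or f. Assumed values:

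| p | s | f = 1 | f = 0.5 | f = 0 |
|---|---|---|---|---|
| 20% | 0.3 | 20% | 13% | 6% |
| 20% | 0.6 | 20% | 16% | 12% |
| 20% | 0.9 | 20% | 19% | 18% |
| 40% | 0.3 | 40% | 26% | 12% |
| 40% | 0.6 | 40% | 32% | 24% |
| 40% | 0.9 | 40% | 38% | 36% |

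For example, 0.20 × (0.5 + 0.5 × 0.3) = 0.13. Recorded incidence cannot exceed p and equals it only if s = 1 or f = 1. The size ranges from trivial to large depending on the assumptions, so none of these figures estimates what this trial would show.

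If s and f are the same in each arm, the bracket multiplies every arm alike. The ratio of recorded rates is then unchanged, and the absolute difference shrinks in the same proportion as the rates.

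**The case against.** The strongest reply has four parts.

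- *Section 7.11 governs method.* Section 3.5 says Table 2 gives the time points and leaves detailed descriptions to the later sections; Appendix B and SAP 8.4 both refer to Section 7.11. Footnote z is then the outlier. This has weight, but footnote z is an explicit current instruction, it agrees with the endpoint, and Section 7.11 does not fully agree with itself.
- *The choice was deliberate.* The Amendment 02 log (Section 16.1) shows pain being taken out of the Section 7.11 list and the spontaneous-report wording being put in. It names footnote z as affected, though the reason given concerns assessment windows. I cite the log for intent only. A deliberate choice would still leave the current footnote unreconciled.
- *Patients are asked anyway.* Section 7.1.2 requires an open-ended adverse event question at each contact, and Appendix B requires a postdose inquiry before the patient leaves at visits 2, 3 and 4. This stands. A reader might infer that sites following Section 7.11 ask nobody, or that pain not volunteered leaves no trace; these provisions rule that out. The contrast is between a general prompt and a pain-specific check at two set times.
- *The comparison is blinded.* All arms receive the same number of injections (Section 3.1), and placebo has the same vehicle and excipients (Section 5.1.2). This also stands. Nothing in the conflict favours one arm.

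The reply that the 1-hour rule and the absent grade can work with volunteered pain is fair as far as it goes: a severe report can arise at 1 hour, and absent can mark resolution. They still fit scheduled assessment better.

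**Conclusion.** The inconsistency is real and lies in current text. It affects how a named safety endpoint is ascertained: recorded pain incidence can vary by site and may be too low. The amount cannot be estimated from the documents, which give no pain rate, no rate of unprompted reporting and no split of sites.

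A reader might go further and infer that the risk difference is understated by some definite fraction. The documents do not support that: any such figure would come entirely from assumed rates and an assumed site split, and monitoring or the case report form, which we have not seen, may produce more uniform practice than the text suggests. Nor do they support systematic bias between arms. That conclusion rests on blinding, equal injection numbers and a similar tendency to report pain in each arm.

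The point warrants a correction to the protocol and SAP. It does not bear on the primary efficacy result.

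**What to change.** Reconcile footnote z, Section 7.11 and SAP 8.4 so that one method of ascertaining pain applies at every site. Either direction removes the contradiction.

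- *Scheduled assessment* fits the existing text best: the endpoint wording, footnote z, the absent grade and the 1-hour rule. Restore pain to the list in Section 7.11 and SAP 8.4, have it checked at the two existing times after each dose, grade it 0 to 3 by Table 5 with absent recorded, and tabulate the grades by treatment. The cost is one question at an assessment staff already perform, one table, and a somewhat higher reported pain rate.
- *Spontaneous reporting*, if that is what the Amendment 02 wording intends, requires footnote z, the endpoint wording in protocol Section 2.1 and SAP Section 1.3, and the 1-hour pain rule to be brought into line. The result should be labelled as spontaneously reported pain. The cost is wording only, but the endpoint then measures something narrower.

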8.1. Pharmacokinetics Assessment

Sampling for pharmacokinetics will be sparse. Thus, the fremanezumab pharmacokinetics samples will be analyzed using a population pharmacokinetics approach and will be reported separately to the clinical study report.

Blood samples [REDACTED] will be collected via venipuncture/indwelling catheter at the time points detailed in [Table 2](#) for plasma concentration measurements of fremanezumab. The dates and times of IMP administration and the date and time of each pharmacokinetics sample will be recorded on the source documentation and transcribed onto the CRF.

Samples from patients who receive active IMP will be analyzed for concentration of fremanezumab using a validated method. Samples from patients who were randomized to receive placebo will not be analyzed. Details on sample handling, storage, shipment, and analysis are given in [Appendix N](#).

8.2. Pharmacodynamics Assessment

Pharmacodynamics parameters are not evaluated in this study.

8.3. Immunogenicity Testing

Blood samples [REDACTED] will be collected via venipuncture or indwelling catheter at the time points detailed in [Table 2](#) for immunogenicity testing.

Samples from patients who receive active IMP will be analyzed for ADA using a validated method. Samples from patients who receive placebo will not be analyzed unless the patient elects to enroll into an available extension study where the patient will receive fremanezumab treatment. In this case, the predose (baseline) sample from the rolled-over placebo patient will be analyzed along with posttreatment samples collected in the extension study and values will be reported in the extension study. Details on sample handling, storage, shipment, and analysis are provided in [Appendix O](#).

8.4. Assessment of Exploratory Biomarkers

Biomarkers are defined as biological substances that monitor physiological effects, assess drug activity, and predict clinical outcome, safety, and response to therapy. Details on sample handling, storage, shipment, and analysis are provided in [Appendix P](#).

CGRP-containing nerve fibers are prevalent in bone tissue and have been hypothesized to be important in the regulation of bone metabolism, response to bone injury, and the perception of bone pain. In vitro, CGRP is anabolic to osteoblasts and can inhibit maturation to osteoclasts. Preclinical studies suggest CGRP antagonism may have benefit in osteoarthritis ([Benschop et al 2014](#)) and bone-related pain [REDACTED]

[REDACTED]

In preclinical models, CGRP can promote angiogenesis in ischemia, capsaicin-induced synovitis, and neovascularization of tumors. [REDACTED]

[REDACTED]

CGRP is known to act directly on macrophage and dendritic cells by inhibiting them from producing inflammatory cytokines and presenting antigens to T cells. It has been hypothesized that CGRP may act as a regulator of the innate immune response. Exploratory analysis will be conducted [REDACTED]

[REDACTED]

The planned biomarker analysis will be detailed in a separate document, which may be updated at a later stage before the analysis to allow updating with new scientific information.

8.5. Pharmacogenomics

For information regarding pharmacogenomic assessments, see [Appendix Q](#). Multiple genetic loci have been identified that could affect the binding affinity of the CGRP-receptor-ligand complex, while other genetic loci have been identified as having roles in migraine and/or headache onset ([Anttila et al 2013](#)). To explore the potential impact of normal variations in these loci on parameters in this study, a blood sample (6 mL) will be collected from each patient (unless the patient declines testing or local regulations prohibit testing) for pharmacogenomic assessment during this study. Pharmacogenomic assessment potentially includes the association analysis of both known and unknown DNA and RNA genetic variations.

8.6. Ancillary Studies – Wearable Sensor Substudy

At selected sites, a subset of patients (n=45, approximately 15 patients from each treatment group) will be asked to wear a sensor monitoring system (digital wearable device) on the wrist to track sleep patterns and activity patterns. [REDACTED]

These changes will be evaluated during days when patients experience CH attacks relative to days free of attacks, and will be evaluated for use as predictors of seasonal onset of new CH epoch. [REDACTED]

Patients with CH describe their attacks to exhibit remarkable circadian and annual periodicity. The attacks are described to strike at predictable times of the day, mostly related to nocturnal sleep, and the clusters of these at specific times of the year ([Barloese 2012, 2015](#), [Rozen and Fishman 2012](#)). CH attacks are also accompanied by systemic manifestations such as agitation and restlessness ([Barloese 2015](#)).

It is anticipated that risks to patients beyond those listed in Section 1.3 are unlikely.

Patients who are able to demonstrate appropriate use of the wearable device and are willing to comply with the requirements for use of the digital wearable device will be given the device and accessories at the baseline visit. The device will be worn continuously throughout the 12-week treatment period, and for patients who continue into the long-term safety study (Study TV48125-CNS-30058), the device will be worn continuously throughout the 40-week treatment period of that study. Device checks and compliance checks will be done at the study center as described in the schedule of events shown in Table 2. The device will be collected at the time the patient discontinues from the study (ie, at the EOT visit if the patient will not continue participating in the substudy during the long-term safety study or at the early withdrawal visit).

The digital wearable device is provided by Philips and will monitor activity during wake periods, which will be used to quantify relative activity. It will also monitor activity during sleep periods, which will be used to quantify sleep-wake parameters. Data will be obtained with an actigraphy device worn on the wrist. Motion data will be analyzed with either standard analysis techniques and/or advanced signal processing algorithms to extract the maximum amount of information from the data. Further information on the device and its use is provided in the substudy manual.

9. STATISTICS

This section describes the statistical analysis as foreseen at the time of planning the study. Changes, additions, and further details about the analyses will be described in the statistical analysis plan. After finalization of the statistical analysis plan, any additional analyses or changes to analyses that may be required will be fully disclosed in the clinical study report.

9.1. Sample Size and Power Considerations

A sample size of 258 patients (86 evaluable patients completing the study per treatment group) will provide at least 90% power to detect a treatment difference of 1 CH attack in the weekly average (assuming a common standard deviation [SD] of 2 CH attacks) at a 2-sided alpha level of 0.05. Assuming a 14% discontinuation rate, approximately 300 patients will be randomized in the trial.

